Title: Exploring the effects of an intravaginal lactic acid gel on the vaginal microbiome

Version Date: November 23, 2022

Principal Investigator: [name] MPH

Co-Investigator(s): [name], DO, [name] MPH

Research associates: [name], [name] and [name] (SRI)

Research Site(s): The Queen's Medical Center, [name]

Abbreviations:

- **BV: bacterial vaginosis**
- **CV: candida vaginitis**
- **HRT: hormone replacement therapy**
- **CST: community state types**

Section I: Purpose and Background

1. Specific aims and objectives:

This project aims to investigate if the contraceptive method, Phexxi, causes changes to the composition of the vaginal microbiome. We hypothesize that regular use of Phexxi will cause increased colonization of lactic acid-producing lactobacilli, which could have positive effects in the way of preventing recurrent episodes of BV and candida infections.

Primary outcomes

- To assess if the use of Phexxi causes changes in the vaginal microbiome
- To assess if the use of Phexxi decreases vulvovaginitis symptoms in study participants

Secondary outcome

- To assess patient satisfaction/acceptability of this intervention as a therapeutic/prophylactic agent for recurrent vulvovaginitis

2. Background, significance, and rationale

Bacterial vaginosis (BV) and candida vaginitis (vaginal yeast infection) are debilitating, long-term conditions which have been associated with decreased confidence and self-esteem, difficulty with sexual intimacy, and decreased quality of life amongst women who suffer from one or both chronically. BV has a particularly high rate of recurrence, with an estimated 30% of infections recurring within three months of treatment, and an estimated 50% of infections recurring within six months of initial treatment¹.

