*Note: NuvaRing is the only medication that will be included in the exclusion criteria. While we will ask all participants to provide a list of medical conditions they have and a list of medications they are currently taking, these will be for the purposes of data analysis, and to account for possible confounders of our data.

*Note: patients do not have to be symptom-free to participate in this study. However, as stated below, if they receive antibiotic/antifungal treatment prior to starting the study, we will ask them to wait 10 days after the completion of the treatment before they collect their first swab, in order to allow for the restoration of their baseline bacterial flora.

3. Vulnerable subjects:

N/A. Pregnancy is listed as an exclusion criteria, and no minors or incarcerated persons will be included in this study.

Section III: Methods and Procedures

1. Study design and methods

This is a single center, prospective trial, which comprises of a pre-post study design will be looking at the vaginal microbiome makeup of participants before and after a four-week course of Phexxi. The primary outcomes will be an increase in lactic acid-forming lactobacilli, as well as a decrease in patient-reported symptoms of vulvovaginitis.

This study will be based at the Queen's Medical Center (QMC), [name]. Eligible patients will be approached by participating clinicians (all doctors providing care at the 1004 clinic, as delineated in the LOA form) to assess interest in study participation.. The principal investigator will review the weekly schedule for the 1004 clinic and alert the attending physicians of patients who may be eligible for the study based on chart review. A HIPAA waiver will be required for this stage of recruitment, as the principal investigator would otherwise not be accessing these patient's charts. The attending physician staffing the 1004 clinic will ask the flagged patients if they are interested in learning about the study and review general study objectives with patients. If the patient is interested in participating, the research associates will approach the patient to more thoroughly screen, then conduct the informed consent process. Informed consent will be collected from every participant prior to the start of the study.

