After obtaining informed consent, the research team will review standardized instructions for using the study medication with the patient and the research associate will provide a take-home kit including all of the study materials, including instructions for collecting each swab (Appendix A) and for returning the samples. Samples will be self-collected by participants at their home at intervals specified in the study instructions. All materials provided to the patient will be pre-labeled with their study ID, protecting each participant's PHI. No collections will take place in-clinic. These materials include all surveys, patient's diary, and all swab vials.

All vaginal swabs must be frozen within 48 hours of collection. As such, the participants will be asked to send their samples within 24 hours in order to give adequate time for delivery to the storage facility and be asked to collect their specimens between Sunday and Thursday so samples can reach the facility during business hours. Freezing will occur at the research site. Each patient's study kit will include a prepaid shipping envelope, which the participant can use to mail or drive their specimen to the research team who will then place it in the freezer until it is ready for analysis.

The first phase of the study will include an assessment and classification of patients' vaginal microbiome prior to receipt of the intervention. To get the best representation of the participant's baseline microbiome, the participant will be asked to collect their baseline swab no sooner than 10 days after menses, as menses-induced changes in the microbiome have been shown to resolve after this time¹². For similar reasons, if participants are being treated with an acute course of antibiotics or antifungals at the time of recruitment, they will be asked to wait 10 days after the completion of their medication course before collecting their baseline swab. There will be two additional time points for collection: collection 2) at the end of the 30 day intervention, and collection 3) 30 days after completion of the intervention.

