The intervention will take place on a rolling basis, as patient participation will have no bearing on other participants. The intervention itself will take place over thirty days. 8 pre-filled vaginal inserters with vaginal gel, will be provided to each of the participants with verbal and written instructions for application. Patients will be instructed to use Phexxi twice per week, on the same days every week. Throughout the 30 days, participants will also be asked to keep a diary of events (Appendix E) occurring when they used the product, such as intercourse or menses, as well as record any symptoms or side effects they noticed when using the product. The diary can be sent back with the second specimen vial. Disposal of the product may be done in a regular waste basket.

Approximately 30 days after completion of the intervention, participants will receive an email reminder to collect and send a third collection swab in (Appendix G) for analysis. This email will also include the link for the third and final set of surveys (B and C).

2. Data analysis and monitoring (include adverse event reporting procedures)

The pre-and post-intervention results will be compared with the subjects to serve as their own controls in this pilot study. To assess for the primary outcomes, each bacteria identified in the NextGen analyses of the composition of the pre-intervention microbiome sampling will be individually named, then classified as either “lactic acid-forming (LAF)” or “not lactic acid-forming (NLF)”. This will allow us to identify which CST each participant falls under prior to the study, and to assess if they can be classified under a different CST at the end of the study. It also allows us to conduct an independent t-test to test for significance between two variables (LAF/NLF) pre and post-intervention.

Demographic data will be collected from patient surveys. Demographic information to be collected will include age, ethnicity, number of reported vaginal yeast infections or BV infections in the last year, type of contraception used, type of diet, and medical comorbidities/current medications. This demographic information will allow us to perform a multiple regression analysis on our data set to account for confounding factors in our study population.

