Survey B, completed at the first, second and third collection time points will assess the symptom profile of each patient. Survey B is modified version of the VSQ (vulvovaginitis symptom questionnaire, which is a validated tool used to assess vulvovaginitis symptoms. A blank space will also be provided to allow for free text answers. These answers will be assessed qualitatively, looking for key themes within the answers provided.

To assess for the secondary outcome, Survey C, delivered at the second and third time point, will ask the patient what their satisfaction and acceptability ratings for Phexxi use as a prophylactic agent for vulvovaginitis are. Survey C is a validated tool, used to measure the acceptability, appropriateness, and feasibility of an intervention. A blank space will also be provided to allow for free text answers. These answers will be assessed qualitatively, looking for key themes within the answers provided.

3. Data storage, security, and confidentiality:

Patient information will be de-identified and connected to a unique Study ID. All identifiable information will be stored in a password protected and encrypted computer in the PI's research office at QMC, which is secured at the 1004 clinic. The signed consent forms will also be stored at the 1004 clinic, in a folder located in a locked office. Only the PI and [name] will have access to the identifiable information. [name], who will be performing analysis using specimens pre-labeled with the study ID, will not have access to participant PHI.

If participants opt, in their initial consent, to receive a copy of their vaginal microbiome results, the results will be sent to them via email, using a QMC email address. In order to encrypt this email, the function [encrypted] will be placed in the subject line.

4. Transition from research participation (if applicable): – Not applicable

5. Study timeline:

As the participation of subjects is not directly reliant on one another, data collection will begin as soon as the first subject is enrolled, and will continue until 30 days after the last subject completes the intervention. We hope for the total timeline to be approximately 1 year, which allow for time for data analysis and write-up of the intervention results.

Section IV: Risk/Benefit Assessment

1. Risk category (Minimal or Greater than Minimal): This study poses minimal risk to the patient.

2. Potential risk(s):

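### Section III.2 words the timing of the two microbiome readouts inconsistently and names no follow-up swab for either

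*Protocol*

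**What the plan says.** The hypothesis in Section I.1 is that "regular use of Phexxi will cause increased colonization of lactic acid-producing lactobacilli". Section III.1 describes a pre-post design looking at the "vaginal microbiome makeup of participants before and after a four-week course of Phexxi". After the baseline swab it plans two more: "collection 2) at the end of the 30 day intervention, and collection 3) 30 days after completion of the intervention".

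Section III.2 turns these swabs into two readouts of the microbiome outcome. For CST, the aim is "to assess if they can be classified under a different CST at the end of the study". For LAF/NLF, in the next sentence, a t-test is to "test for significance between two variables (LAF/NLF) pre and post-intervention". Neither sentence gives a collection number.

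Section III.5 says that data collection "will continue until 30 days after the last subject completes the intervention", which is when collection 3 falls. Appendix E, the participant diary, asks for the diary to come back with the second specimen and dates that 30 days after the drug has been finished. Section III.1 puts the second specimen at the close of the intervention.

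**The concern.** Two readouts of one outcome carry different time phrases in the same paragraph. Collections 2 and 3 answer different questions. The first shows the microbiome at the end of four weeks of use. The second shows what is left about a month after use stops. The hypothesis is about use, and no listed outcome mentions persistence after stopping.

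Two things are at stake. If an effect fades once the gel is stopped, a CST result read only at collection 3 could be reported as no change, under an aim that asks about use. And because the planned test compares two time points while three swabs are taken, one later swab has to be chosen. The protocol does not choose, so the choice can be made after the results are known, in a single-arm study of about 20 evaluable women.

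**Working it through.** No sample size or power figure depends on this point. The check is a comparison of the wording, some timeline arithmetic and one error-rate bound.

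**Wording side by side**

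| Place | Time point stated | Which later swab fits |
|---|---|---|
| Section I.1, hypothesis | regular use | collection 2 most directly |
| Section III.1, design | before and after the four-week course | 2 or 3 |
| Section III.2, CST | end of the study | 3, read literally |
| Section III.2, LAF/NLF | pre and post-intervention | 2 or 3 |
| Section III.1, Survey B | before, immediately after and 30 days after | all three named |

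The literal reading of the CST phrase has support elsewhere. Section III.5 runs data collection to collection 3. Section III.1 calls the surveys at that point the final set. The reminder email in Appendix G treats that swab as the last one and its surveys as what completes the study.

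**Timeline**

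- Inputs from Section III.1: eight applicators, two per week, a 30-day intervention, and a third swab 30 days later.
- Course covered: 8 / 2 = 4 weeks = 28 days.
- Collection 2: about day 30. Collection 3: about day 30 + 30 = day 60.
- Assumed day of last application: 25 to 28. Time off the gel at collection 3: 60 − 28 = 32 to 60 − 25 = 35 days.

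**Choice between two later swabs**

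- Assumptions: each comparison with baseline is tested at 5% (the protocol states no level for this test), there is no true effect, and a significant result at either swab is reported as the primary one.
- Fully correlated tests: 5%.
- Independent tests: 1 − 0.95² = 1 − 0.9025 = 9.75%.
- Both comparisons use the same women and the same baseline swab, so positive correlation is expected and the true figure should lie below 9.75%, nearer 5%.

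**Fading of the effect**

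If a fraction r of the shift at collection 2 remains at collection 3, the later swab shows r times that shift. The documents give no value for r, so it could lie anywhere from 0 to 1, and no size is claimed here.

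**The case against.** A reader might infer that the protocol fixes the microbiome outcome at two conflicting times. It does not. The design sentence and the LAF/NLF sentence both use wording that fits either later swab, so neither contradicts the other, and neither ties LAF/NLF to the end of the course.

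A reader might also infer that the CST result necessarily measures persistence and says nothing about use. That depends on the literal reading. The same sentence speaks of CST before the study, although the baseline swab is taken after consent and Section III.1 places it in the study's first phase. The study may therefore loosely mean the intervention there. Collection 2 is sequenced too, and nothing stops a CST being assigned to it. This part of the objection stands, and the point is limited accordingly.

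Three further arguments carry some weight. CST is not itself a named primary outcome; it is one of the readouts offered for the microbiome outcome. A reading after stopping bears on the prophylaxis aim in Section I.3, so collection 3 is of real interest. And no rule of picking the better swab is written anywhere, so the 9.75% is a bound under an assumption.

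The last argument is that choosing the primary visit is commonly left to a statistical analysis plan. It would succeed if the protocol were silent. Here the protocol states a time point for CST, words it differently from the one beside it, and names exact time points for the surveys. The defect lies in what is written.

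**Conclusion.** The point holds as an inconsistency and ambiguity of timing in Section III.2. Taken literally, CST change is judged about a month off the gel (32 to 35 days after the last application, if that falls on days 25 to 28), while the hypothesis concerns regular use. The LAF/NLF test may use either later swab. Leaving the swab open puts the false-positive chance above 5% and at most at 9.75%, under the assumptions listed, with correlation pulling it towards 5%.

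The Appendix E conflict makes matters worse. A participant who follows the diary's wording could take her second swab when the third is due, and the end-of-course sample would be lost.

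The documents do not support the stronger claims that two times are fixed in contradiction, or that CST cannot inform on the effect of use. Correcting the wording is worthwhile and proportionate.

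**What to change.** In Section III.2, replace the end-of-study phrase for CST and the post-intervention phrase for LAF/NLF with one named collection that serves both. Collection 2 against baseline matches the stated hypothesis and the before-and-after design. State that collection 3 is reported separately, as a secondary measure of persistence after stopping.

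Reconcile Appendix E with Section III.1 so that the second specimen has a single date. Otherwise the named collection would itself be dated in two ways.

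The cost is a few sentences of protocol and diary text. All the swabs and their sequencing are already planned. The real price is that a favourable result at collection 3 could then be reported only as secondary.

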Appendix G: Reminder email

Hello (name),

Thank you for your participation in our research study on how Phexxi can change the vaginal microbiome. It has now been approximately 30 days since you completed your course of Phexxi. It is now time for you to submit your last swab to us. Please follow the instructions provided in the pre-packaged envelope to obtain an

adequate specimen collection. As a reminder, these specimens must be sent to us within 24 hours of collection.

Additionally, please fill out the attached surveys in order to complete this study. On receipt of your completed surveys and your final swab, I will send you your \$10 remuneration. Additionally, if you originally indicated that you would like a copy of your results, I will send those to you via email once the analysis of data has been completed.

Thank you again for your time and hard work!

Best Regards,
[name]

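### Section III.1 lets a participant follow every collection and sending rule and still have a mailed swab miss the 48-hour freezing limit

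*Protocol*

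**What the plan says.** Protocol Section III.1 (Study design and methods) sets these rules together:

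- **Limit.** "All vaginal swabs must be frozen within 48 hours of collection".
- **Place.** "Freezing will occur at the research site", so the clock runs until the swab has reached the site.
- **Sending.** "the participants will be asked to send their samples within 24 hours in order to give adequate time for delivery to the storage facility".
- **Collection days.** Participants will "be asked to collect their specimens between Sunday and Thursday so samples can reach the facility during business hours".
- **Transport.** Each kit holds a "prepaid shipping envelope, which the participant can use to mail or drive their specimen to the research team". No carrier, service level or transit time is given.

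Appendix G, the reminder for the third swab, repeats the sending rule: "these specimens must be sent to us within 24 hours of collection". It does not mention the days of the week, and it refers the participant to instructions in the pre-packaged envelope.

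**The concern.** The weekday window and the 24-hour sending rule are there to deliver the 48-hour limit. Thursday is the last allowed day, and a full 24 hours to send moves posting to Friday. The limit then expires on Saturday, when a site keeping ordinary business hours is closed. The unstated transit time is a second gap. Of the 48 hours, 24 may be used before the swab is even sent, which leaves 24 for delivery and freezing.

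Sequencing of these swabs is the only measurement of the microbiome primary outcome, and Section III.2 makes each woman her own control. If her baseline swab is frozen promptly and a later one is not, the difference in handling becomes part of her pre/post comparison, and there is no control group against which to see it. Section III.1 calls for no record of collection or freezing times, so a breach could pass unnoticed.

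**Working it through.** **Inputs from the Protocol (Section III.1 unless stated).** Limit 48 h; sending allowed up to 24 h; collection Sunday to Thursday; freezing at the site; three swabs per woman; 22 women enrolled, for 20 after an expected 10% loss (Section II.1).

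**Assumptions not in the Protocol.** Receipt Monday to Friday from 08:00; mail delivered at 10:00; collection on the hour from 07:00 to 22:00 (16 collection times); mail moves on each day it is posted. Saturday receipt is tested separately.

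The 48 hours is a set limit, not a derived figure, so there is nothing to reproduce. The check is clock arithmetic.

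**1. Thursday swab mailed on Friday.**
- Deadline: Thursday + 48 h = Saturday.
- Earliest arrival by mail: Saturday. Earliest receipt: Monday.
- Thursday 23:59 to Monday 08:00 is about 80 h; Thursday 00:00 to Monday 08:00 is 104 h. The excess is 80 − 48 = 32 h to 104 − 48 = 56 h.
- Whatever the opening hour, Thursday midnight to the first minute of Monday is already 72 h.

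**2. Thursday swab, other routes (collection 07:00 to 22:00).**

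| Route | Hours to receipt | Share within 48 h |
|---|---|---|
| Posted Thursday, next-day delivery | 12–27 | 100% |
| Posted Thursday, two-day delivery | 82–97 | 0% |
| Posted Friday, next- or two-day delivery | 82–97 | 0% |
| Posted Friday, next-day delivery, Saturday receipt | 36–51 | 81% |
| Posted Friday, two-day delivery, Saturday receipt | 82–97 | 0% |

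A swab driven in during Friday business hours is also within the limit.

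**3. Other allowed days, posted at 24 h.**
- Next-day delivery: a swab taken at hour h and delivered at 10:00 two days later takes 48 + 10 − h hours. That is 58 − 22 = 36 to 58 − 7 = 51 h. It meets the limit only if h is 10 or later, which is 13 of the 16 collection times (81%).
- Two-day delivery: 72 + 10 − h, which is 82 − 22 = 60 to 82 − 7 = 75 h for Sunday to Tuesday. For Wednesday, arrival falls on Saturday and receipt on Monday, giving 106–121 h. None meets 48 h.

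**4. How many swabs are exposed to the Thursday route.** With equal use of the five days, no dropout, and the weekday of one swab independent of the other:
- Swabs: 22 × 3 = 66; 66 × 0.2 = 13.2. With 20 completers: 60 × 0.2 = 12.
- Baseline/collection-2 pairs with at least one Thursday swab: 1 − 0.8² = 36%.

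These count Thursday swabs, not late ones. If half of them are driven in or posted the same day with next-day delivery, the figures fall to 66 × 0.1 = 6.6 swabs and 1 − 0.9² = 19% of pairs. If all are, both are zero.

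**The case against.** The strongest reply is that a Thursday breach needs several things at once: a Thursday collection, mail rather than hand delivery, posting on Friday rather than Thursday, and no Saturday receipt. Section III.1 expressly offers driving the swab in, and it does not define business hours. This stands. It makes the breach conditional, but it does not remove it, because nothing in the Protocol rules out any of those steps or provides for weekend receipt.

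A reader might infer that the participant-facing texts make matters worse, since Appendix A covers only swab technique and Appendix G gives only the 24-hour rule. The documents do not support that. Section III.1 says the kit also holds instructions for returning samples. These are not among the appendices, and they may carry the weekday rule.

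A reader might also infer that late swabs are unfit or that the results will be biased. The limit is worded as mandatory, but no rejection rule is stated. Nothing says how a delay of this length alters composition, and the stabilising effect, if any, of the transport tube's contents is not described. Nor is there any sign that the weekday of collection differs systematically between baseline and follow-up. Extra noise in some pairs is as plausible as a shift. The symptom outcome is untouched.

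Finally, this can be called a shipping detail in a small pilot. It is one, but it bears on the only measurement of a primary outcome and costs little to put right.

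**Conclusion.** The point holds in a conditional form: the collection-day, sending and freezing rules in Section III.1 do not together deliver the 48-hour limit.

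- A Thursday swab mailed on Friday complies with every rule given to the participant. With Monday-to-Friday receipt and an 08:00 opening it is frozen 80 to 104 h after collection. This rests on the ordinary meaning of business hours, which the Protocol does not define.
- The gap is not only a Thursday one. With two-day mail, a swab from any allowed day posted at 24 h takes 60 h or more.
- About 13 of 66 swabs and 36% of baseline/collection-2 pairs are ceilings for the Thursday route, given equal use of the days, independence and no dropout. It would be wrong to read them as the number of late swabs, which is unknown.
- The effect on the microbiome results cannot be sized from the documents.

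**What to change.** Reconcile the three rules in Section III.1:

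- Ask for posting on the day of collection with a next-day service, or for hand delivery in business hours within the limit. Name the service and state the site's receiving days.
- Do not allow mailed Thursday swabs unless they are posted the same day for Friday receipt. Dropping Thursday alone would not be enough while transit time is open.
- Check the remaining days against the carrier chosen. If mail is not picked up on Sundays, a Sunday swab behaves like one posted at 24 h (36–51 h with next-day delivery).
- Put the weekday and same-day rule in the Appendix G reminder, and make sure the kit's return instructions carry it.
- Record collection and freezing times for every swab, and repeat the microbiome analysis without swabs frozen after 48 hours. The detail of that analysis can sit in the statistical analysis plan.

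The cost is instruction wording, two recorded times per swab and one further analysis. The downside is a slightly narrower collection and posting window for participants.

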Appendix B Patient demographic survey

Demographic Survey

Subject ID:

1: What is your age?:

2: What is your race?

3. Are you Hispanic/Latinx?

4.: How many yeast infections or episodes of bacterial vaginosis (BV) have you had in the last year?

5: Are you on any kind of birth control? If yes, what kind?

6: In the next portion, please describe what kinds of food you normally eat in a typical day. In addition to meals, please include snacks. If you are currently on a specific type of diet, please state that here.

Breakfast

Lunch

Dinner

Other

7 What other medical conditions have you been diagnosed with? If none, please write, "none".

8: Please list any medications/supplements you are currently taking. If none, please write, "none".

Appendix C. Survey to assess vulvovaginitis symptoms. Modified version of the Vulvovaginitis Symptom Questionnaire (VSQ)

During the past week, have you been bothered by:

1. Your vulva itching? 0 No 1 Yes

2. Your vulva burning or stinging? 0 No 1 Yes

3. Your vulva hurting? 0 No 1 Yes

4. Your vulva being irritated? 0 No 1 Yes

5. Your vulva being dry? 0 No 1 Yes

6. Discharge from your vulva or vagina? 0 No 1 Yes

7. Odor from your vulva or vagina? 0 No 1 Yes

8. Worry about your vulvar symptoms? (for example, that it will spread, get worse, scar, etc.) 0 No 1 Yes

9. The appearance of your vulva? 0 No 1 Yes

10. Frustration about your vulvar symptoms? 0 No 1 Yes

11. Embarrassment about your vulvar symptoms? 0 No 1 Yes

- 12. The effects of your vulvar symptoms on your interactions with others? 0 No 1 Yes
- 13. The effects of your vulvar symptoms on your desire to be with people? 0 No 1 Yes
- 14. Your vulvar symptoms making it hard to show affection? 0 No 1 Yes
- 15. The effects of your vulvar symptoms on your daily activities? 0 No 1 Yes
- 16. Your vulvar symptoms affecting your desire to be intimate? 0 No 1 Yes
- 17. Are you currently sexually active with a partner?
 No → Thank you. You are done with this questionnaire. Yes → Please proceed with the next 4 questions
- 18. The effects of your vulvar symptoms on your sexual relationships? 0 No 1 Yes
- 19. Your vulvar symptoms causing pain during sexual activity? 0 No 1 Yes
- 20. Your vulvar symptoms causing dryness during sexual activity? 0 No 1 Yes
- 21. Your vulvar symptoms causing bleeding during sexual activity? 0 No 1 Yes

Please use the space below to list any vulvar/vaginal symptoms you are experiencing which have not already been listed.

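### No instrument clearly asks about antibiotic or antifungal use between collections 2 and 3, and Appendix E misdates the return of the diary and second specimen

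*Protocol*

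**What the plan says.** **Baseline.** Section III.1 asks women on an acute course at recruitment to wait: "they will be asked to wait 10 days after the completion of their medication course before collecting their baseline swab". The notes in Section II.2 say the same: "if they receive antibiotic/antifungal treatment prior to starting the study, we will ask them to wait 10 days after the completion of the treatment". The reason given there is recovery of the usual flora. The same notes say of the medical-condition and medication lists: "these will be for the purposes of data analysis, and to account for possible confounders of our data". The question itself is Appendix B item 8, "Please list any medications/supplements you are currently taking". It belongs to the demographic survey given in the first phase only.

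**During the intervention.** Section III.1: "Throughout the 30 days, participants will also be asked to keep a diary of events". The diary form (Appendix E) names new medications as an example of an event to write down. On its return, Section III.1 says: "The diary can be sent back with the second specimen vial". Section III.1 places collection 2 at the end of the 30-day intervention and collection 3 30 days later. Appendix E also ties the diary to the second specimen, but dates that return 30 days after the drug is finished.

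**Collection 3.** Of the reminder email, Section III.1 says: "This email will also include the link for the third and final set of surveys (B and C". Survey B (Appendix C) has 20 symptom items, one item on sexual activity and a free-text box: "Please use the space below to list any vulvar/vaginal symptoms you are experiencing which have not already been listed". Survey C (Appendix D) has 12 statements about Phexxi and a box for comments on using it. The email text (Appendix G) asks for the swab and the surveys and does not mention treatment.

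**The concern.** Each woman is her own control (Section III.2) and there is no comparison arm, so a competing cause of change can be recognised only if it is recorded. The protocol names one such cause, recent antibiotic or antifungal treatment, and guards the baseline swab against it. For the month before collection 3 it neither guards against it nor clearly asks about it.

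Two things are at stake:

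- **Interpretation of collection 3.** A shift in lactic acid-forming bacteria, or in symptoms over the past week, that follows treatment could not be separated from a lasting effect of Phexxi. Survey B measures a primary outcome and is given at this time point.
- **The event of interest.** Section I.3 states an aim of exploring prophylaxis against recurrent BV and yeast infection. A recurrence treated in the follow-up month is direct evidence on that aim, yet it comes to light only if the woman volunteers it.

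Treatment in that month is foreseeable. Entry requires at least two treated episodes in the past year (Section II.2). Nothing in the protocol bars treatment during participation.

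**Working it through.** **1. Does any route cover the interval from collection 2 to collection 3?**

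| Route | What it asks | Period covered |
|---|---|---|
| Appendix B item 8 | Current medications | Baseline only |
| Diary (Appendix E) | Other events, with new medications as an example | The 30 intervention days; back with specimen 2 |
| Survey B (Appendix C) | Symptoms in the past week; free text on unlisted symptoms | No treatment question |
| Survey C (Appendix D) | Views on Phexxi; free text on experience of using it | No treatment question |
| Reminder email (Appendix G) | Swab and surveys | No treatment question |
| Chart review (Sections III.1, V.2) | Eligibility | Recruitment only; a chart may miss over-the-counter products |

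No row clearly covers the follow-up month. The diary row depends on how the Appendix E date is read (see the objection).

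**2. How often might it matter?** The protocol gives no figure on this point, so the following is for scale only.

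Inputs from the protocol:
- BV recurrence of 30% within three months and 50% within six months (Section I.2).
- 20 women after drop-out (Section II.1). The smallest n with a 95% chance of showing at least one problem of 15% prevalence is ln(0.05)/ln(0.85) = 18.4, so 19. The stated 20 is close and serves here only as the denominator.

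Assumptions not in the protocol:
- constant hazard counted from baseline (Section I.2 counts from treatment);
- no protective effect of the gel;
- share of women carrying the BV rate 50% to 100%, and share of recurrences treated 50% to 100%;
- treatment starting at recurrence, with a course of 1 to 7 days;
- swab 3 on day 60; first recurrences only; candida left out because no recurrence rate is given.

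*Treated first recurrence in days 31 to 60*
- Monthly hazard h = −ln(0.70)/3 = 0.1189.
- exp(−h) − exp(−2h) = 0.8879 − 0.7884 = 0.0995.
- From 50% in six months: h = ln(2)/6 = 0.1155, giving 0.8909 − 0.7937 = 0.0972.
- Both shares 100%: 20 × 0.0995 = 1.99 women; chance of at least one 1 − (1 − 0.0995)^20 = 0.88.
- Both shares 50%: 0.0995 × 0.25 = 0.0249; 20 × 0.0249 = 0.50 women; chance of at least one 0.40 (0.39 with the six-month rate).

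*Swab 3 during a course or within 10 days after it*
- The course must have begun in the last 11 days (1 + 10) to 17 days (7 + 10) before day 60.
- 11 days: exp(−49h/30) − exp(−2h) = 0.8235 − 0.7884 = 0.0351, or 0.70 of 20.
- 17 days: exp(−43h/30) − exp(−2h) = 0.8433 − 0.7884 = 0.0549, or 1.10 of 20.
- Both shares 50% (× 0.25): 0.18 to 0.27 of 20.
- Overall range: about 0.2 to 1.1 of 20.

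*Sensitivity to the clock.* If the hazard starts at collection 2 instead, 30-day recurrence is 1 − 0.70^(1/3) = 11.2%, or 2.2 of 20 at full shares.

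**3. The Appendix E date.** Section III.1 puts specimen 2 at the end of the intervention, about day 30. Appendix E puts it, with the diary, 30 days after the last dose, about day 60, which is when specimen 3 is due. Both cannot be right.

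**The case against.** - **A reader might infer that nothing at all is recorded.** That is too strong. A woman who follows the date in Appendix E would still hold a diary prompting for new medications during the follow-up month. The likelier reading is the other one, because the same sentence links the diary to the second specimen and Section III.1 confines it to the intervention. The claim is therefore that no instrument *clearly* covers the interval.
- **A reader might infer that the main before-after result is compromised, or that a collection 3 change would be credited to Phexxi.** The documents do not support this. Section III.1 defines the comparison as before and after the four-week course, so collection 2 is the main after point, and medication there can largely be captured in the diary. The protocol never says how a collection 3 change will be attributed. What stands is that the data could not separate the two explanations.
- **The baseline wait creates no duty at follow-up.** This is correct. A wait to characterise baseline does not commit the protocol to the same rule later, where a treated recurrence may be part of the outcome. The case is for recording treatment, not for delaying swabs.
- **Adverse-event reporting may catch some cases.** Appendix F lists BV (8.4%) and mycotic infection (9.1%) as reactions, and Section IV.3 requires withdrawal and reporting when side effects occur. That process centres on stopping the drug and does not ask about treatment in the drug-free month. It narrows the gap without closing it.
- **Flags and supplementary comparisons belong in an analysis plan.** This is true, and their absence is not criticised here. What is asked of participants, however, is fixed in these appendices, and no analysis plan can recover exposure that was never asked about.

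**Conclusion.** The point holds as a minor one, in two parts.

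- **Survey item: a cheap improvement.** The protocol regards recent treatment as disturbing the flora and lists medications to handle confounding, but its instruments do not clearly ask about treatment in the follow-up month. This limits what collection 3 can show and leaves treated recurrences uncounted. No size or direction of bias is claimed.
- **Appendix E date: wrong as written.** It is an instruction to participants that contradicts Section III.1, and following it could move the diary or specimen 2 to about day 60.

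The first part rests on reading the instruments, not on the arithmetic. The illustrative counts (0.5 to 2.0 treated recurrences and 0.2 to 1.1 affected swabs among 20 women) depend on the assumptions listed. The course length and both shares come from outside the protocol. The smaller range is the one that bears on the flora measurement; the larger bears on counting recurrences.

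**What to change.** 1. Add one item to Survey B at collections 2 and 3: any antibiotic or antifungal since the last swab (oral or vaginal, prescription or over-the-counter), with the reason and the date of the last dose.
2. Use the answers to report how many women were treated for BV or yeast, and to flag swabs taken during or within 10 days after a course. Keep swabs on schedule and keep the all-women result as the main one. A comparison without flagged swabs may sit beside it, but it drops prophylaxis failures and may therefore favour Phexxi.
3. Correct Appendix E so that the diary and specimen 2 are returned at the end of the 30-day intervention.

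The cost is one survey item at two time points and one corrected line, with no change to care, swab schedule or sample size. The drawback is that the answer relies on about 30 days of recall. The item must be in place before follow-up data are collected.
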